9.7 HIV counseling and testing

HIV counseling will be performed in compliance with the CDC's guidelines or other local guidelines for HIV counseling and referral. HIV testing will be performed in accordance with the current HVTN HIV testing algorithm following enrollment.

Participants will be counseled routinely during the trial on the avoidance of HIV infection.

Potential participants identified as being HIV infected during screening are not enrolled. Potential and enrolled participants identified as being HIV-infected will be referred for medical treatment, counseling, and management of the HIV infection. Participants who are found to be HIV-infected after enrollment will not receive any additional study product but will continue to be followed in the study for safety assessments. These individuals may also be referred to appropriate ongoing clinical trials or observational studies.

It is theoretically possible that anti-HIV mAb administration may cause common antibody tests to show that someone is HIV-negative, even if they are actually infected. An anti-HIV mAb is not likely to directly reduce or inhibit the assays used to detect HIV-1 infection.

9.7.1 Study product–related seroreactivity

Human sera containing purified VRC01 at concentrations up to 200 mcg/mL have been tested using a variety of commercially available HIV test kits without any indication of reactivity. For this reason, we do not anticipate that receipt of VRC01/VRC01LS will cause a reactive result on currently available HIV test kits, but this remains a theoretical possibility.

Because this possibility cannot be categorically eliminated, study staff will advise study participants to confine their HIV testing while in the study to that provided through the CRS. Staff will also inform study participants of the likelihood of routine HIV testing being offered or performed outside the study CRS at emergency rooms, clinics, and medical offices, and will inform participants of their right to opt out of HIV testing outside the study site. CRS staff should inform study participants if local and/or state/regional policies and regulations permit medical providers to perform HIV testing without first informing patients. If this is the case, then CRS staff should advise study participants that they may decline testing preemptively. CRS staff should also inform participants if positive results must be reported to local public health authorities. CRS staff should provide participants with CRS contact information and should encourage participants to ask medical providers to contact the CRS. The CRS can verify that the participant is in an HIV mAb clinical trial and should only be tested at the study CRS.

Study staff should also stress that the study product is completely cleared from the body within a few months, so even the theoretical risk of VRC01/VRC01LS causing a misleading HIV test result will disappear before their final scheduled clinic visit.

9.8 Contraception status

Contraception status is assessed and documented at every scheduled clinic visit for a participant who was born female and who is sexually active in a way that could cause that participant to become pregnant. Prior to enrollment and throughout the study, staff will ask participants to verbally confirm their use of adequate contraceptive methods. A participant who was born female and is sexually active in a way that could cause that participant to become pregnant should be reminded at all scheduled clinic visits of the importance of using contraception and should be referred to specific counseling, information, and advice as needed. (Specific contraception requirements are listed in Section 7.1). This reminder should be documented in the participant's study record.

Self-reported infertility—including having undergone bilateral oophorectomy or tubal ligation—must be documented in the participant’s study record.

9.9 Urinalysis

Dipstick testing may be performed in the clinic or the lab, as long as the required elements (glucose, protein, and hemoglobin) are tested. The examination is performed on urine obtained by clean catch.

If the screening dipstick is transiently abnormal due to non-urinary bleeding, eg, uterine or vaginal bleeding or spotting or infection, document this issue in the participant’s source documentation. For infection, provide appropriate treatment and/or referral. Following resolution, repeat the dipstick and, if within the eligibility limits specified in the protocol, the participant may be enrolled.

Follow-up urinalysis should be deferred if a participant is experiencing non-urinary bleeding (eg, menstruating), but should be performed as soon as possible. If a follow-up dipstick is abnormal due to a participant’s menstrual period, document in the comment section of the case report form (CRF) and repeat the dipstick once the participant is no longer menstruating. A micro-urinalysis is not required.

9.10 Assessments of reactogenicity

For all participants, baseline assessments are performed before and reactogenicity assessments are performed after infusions per SSP. All reactogenicity symptoms are graded according to the Division of AIDS Table for Grading the Severity of Adult and Pediatric Adverse Events, Corrected Version 2.1, July 2017, except as noted in Section [11.2.2](#).

The reactogenicity assessment period is 3 full days following each infusion per the assessment schedule shown in [Table 9-3](#). Participants are instructed to record symptoms using a postinfusion memory tool. Contacts between the participant and the site staff should take place daily during the assessment period. Clinic staff will follow new or unresolved reactogenicity symptoms present at day 3 to resolution. Participants are instructed to contact the clinic for events that arise during the period between infusions and the next scheduled visit. In general, a participant who self-reports any postinfusion reaction greater than mild is seen by a clinician within 48 hours after onset, unless the reaction is improving and/or has completely resolved.

Reactogenicity events are reported using CRFs that correspond to the time of assessment in [Table 9-3](#). Reactogenicity assessments include assessments of systemic and local symptoms and infusion-related lesions. Events not listed on a CRF, or with an onset after the reactogenicity assessment period (day of infusion

and 3 full days after), or those meeting SAE/adverse events requiring expedited reporting to DAIDS criteria, are recorded on an adverse event log form.

Table 9-3 Schedule of reactogenicity assessments

Day	Time	Performed by
0 ^a	Baseline: before study product administration	HVTN CRS staff
	Early: 25-60 minutes after all infusions	HVTN CRS staff
	Between early assessment and 11:59pm day 0	HVTN CRS staff or participant
1	Between 12:00am and 11:59pm day 1	HVTN CRS staff or participant
2	Between 12:00am and 11:59pm day 2	HVTN CRS staff or participant
3 ^b	Between 12:00am and 11:59pm day 3	HVTN CRS staff or participant

^a Day of study product administration

^b New or unresolved reactogenicity symptoms present on day 3 are followed until resolution

9.10.1 Assessment of systemic and local symptoms

Systemic symptoms include increased body temperature, malaise and/or fatigue, myalgia, headache, chills, arthralgia, nausea, pruritus, diarrhea, and vomiting. Local symptoms include pain and/or tenderness proximal to the infusion site. The daily maximum severity reached for each symptom during the assessment period is reported.

Body temperature is measured by oral or infrared thermometry and reported in degrees Celsius. If temperature is measured in Fahrenheit, the conversion to Celsius should be documented in the participant's chart note. A measurement is taken once daily during the assessment period and should be repeated if participant is feeling feverish.

9.10.2 Assessment of infusion site

Infusion site reactions may include redness or erythema and induration or swelling. The maximum horizontal and maximum vertical measurements for all infusion site reactions are recorded.

All infusion site reactions are monitored until resolution. Areas greater than 25 cm² are followed daily; otherwise, the frequency of follow-up is based on clinician judgment.

9.11 Visit windows and missed visits

Visit windows are defined in HVTN 116 Study Specific Procedures. For a visit not performed within the window period, a Missed Visit form is completed. If the missed visit is one that required safety assessments or local safety labs, HVTN

CRS staff should attempt to bring the participant in for an interim visit as soon as possible.

Procedures performed at an interim visit are usually toxicity/safety assessments (including local safety labs) and HIV testing. With the exception of HIV testing, these procedures are performed only if they were required at the missed visit or if clinically indicated. HIV testing may be performed as deemed appropriate by the study staff. If a participant missed an infusion visit or if infusions must be permanently discontinued, see Section 7.3.2 and Section 7.3.3 for resolution.

9.12 Early termination visit

In the event of early participant termination, site staff should consider if the following assessments are appropriate: a final physical examination, clinical laboratory tests (including urine dipstick, CBC with differential, and chemistry panel), pregnancy testing, social impact assessment, biopsy acceptability questionnaire, and HIV test. For participants who have a confirmed diagnosis of HIV infection, see Section 9.14.

9.13 Pregnancy

If a participant becomes pregnant during the course of the study, no more infusions of study product will be given and no more mucosal biopsies will be collected during the pregnancy, but remaining visits and other study procedures should be completed unless medically contraindicated. For participants who are no longer pregnant, see Section 7.3.1. If the participant terminates from the study prior to the pregnancy outcome, the site should make every effort to keep in touch with the participant in order to ascertain the pregnancy outcome.

9.14 HIV infection during the study

If a participant becomes HIV-infected during the course of the study, no additional study product will be administered. Participants will be encouraged to continue scheduled study visits for up to 16 weeks following their last study product administration. Follow-up duration for participants diagnosed with HIV infection may be adjusted in consultation with the CRS investigator and the HVTN 116 PSRT (eg, to avoid interference with participant initiation of HIV treatment). At post-infection follow-up visits, only specimens required for protocol-specified safety laboratory tests will be collected; in addition, some clinic procedures may be modified or discontinued (see [Appendix H](#), [Appendix I](#), [Appendix J](#), [Appendix K](#), [Appendix L](#), [Appendix M](#), [Appendix N](#), and [Appendix O](#)).

10 Laboratory

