7.3.3 Discontinuing study product administrations for a participant

Under certain circumstances, an individual participant's infusions will be permanently or temporarily discontinued. Specific events that will result in stopping a participant's infusion schedule include:

- Co-enrollment in a study with an investigational research agent (rare exceptions allowing for the continuation of infusions may be granted with the unanimous consent of the HVTN 116 PSRT).
- Clinically significant condition (ie, a condition that affects the immune system or for which continued infusions and/or blood draws may pose additional risk), including but not limited to the following:
 - Pregnancy (infusions will be stopped while a participant is pregnant. If the participant is no longer pregnant and can be infused within an appropriate visit window, infusions may resume, see Section [7.3.1](#));
 - HIV infection;
 - Any grade 4 local or systemic reactogenicity symptom, lab abnormality, or AE that is subsequently considered to be related to study product administration;

- Any grade 3 lab abnormality or other clinical AE (exception: fever or vomiting and subjective local and systemic symptoms) that is subsequently considered to be related to study product administration; or
- Clinically significant type 1 hypersensitivity reaction associated with study product administration. Consultation with the HVTN 116 PSRT is required prior to subsequent infusions following any type 1 hypersensitivity reaction associated with study product administration; or
- Investigator determination in consultation with Protocol Team leadership (eg, for repeated nonadherence to study staff instructions).

Participants discontinuing study product for reasons other than HIV infection should be counseled on the importance of continuing with the study and strongly encouraged to participate in follow-up visits and protocol-related procedures per the protocol for the remainder of the trial, unless medically contraindicated.

Participants diagnosed with HIV infection during the study should be encouraged to participate in follow-up visits as indicated in Section 9.14.

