7.3.5 Discontinuing biopsy collections for a participant

An individual participant's biopsy collections will be permanently discontinued under certain circumstances, including:

- Increase in risk of HIV infection, as indicated by:
 - New diagnosis of chlamydia, gonorrhea, syphilis, or any other disease that, in the clinician's opinion may indicate an increased risk of HIV infection

- Change in HIV risk behavior
- HIV infection
- Any medical condition that presents a contraindication for biopsies (eg, a condition requiring anticoagulants), in consultation with the PSRT
- Investigator determination in consultation with the PSRT and/or Protocol Team leadership (this may include, but is not limited to, situations in which no tissue Ab levels were detected at a previous visit)
- The participant is no longer willing to provide biopsies

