8.1 Infusion regimen

The schedule of infusions is shown in [Section 3](#) and additional information is given below. The study is open label.

Group 1

Treatment 1 (T1): VRC01 (VRC-HIVMAB060-00-AB) 10 mg/kg to be administered IV in 100 mL of Sodium Chloride for Injection USP, 0.9% at Month 0, Month 2, Month 4, and Month 6.

Group 2

Treatment 2 (T2): VRC01 (VRC-HIVMAB060-00-AB) 30 mg/kg to be administered IV in 100 mL of Sodium Chloride for Injection USP, 0.9% at Month 0, Month 2, Month 4, and Month 6

Group 3

Treatment 3 (T3): VRC01LS (VRC-HIVMAB080-00-AB) 30 mg/kg to be administered IV in 100 mL of Sodium Chloride for Injection USP, 0.9% at Month 0, Month 3, and Month 6

Group 4

Treatment 4 (T4): VRC01 (VRC-HIVMAB060-00-AB) 30 mg/kg to be administered IV in 100 mL of Sodium Chloride for Injection USP, 0.9% at Month 0.

Group 5

Treatment 5 (T5): VRC01LS (VRC-HIVMAB080-00-AB)30 mg/kg to be administered IV in 100 mL of Sodium Chloride for Injection USP, 0.9% at Month 0.

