Social impact assessment questionnaire	—	—	—	—	—	X	—	—	—	—	—	—	X	—	—	—	X	—	—	—	
Acceptability questionnaire	—	—	X	—	—	—	—	—	—	—	—	—	—	—	X	—	X	—	—	—	
Concomitant medications	X	X	X	X	X	X	X	—	X	—	X	X	X	X	X	X	X	—	—	—	
Intercurrent illness/adverse experience	—	X	X	X	X	X	X	—	X	—	X	X	X	X	X	X	X	—	—	—	
HIV infection assessment ^f	—	—	—	—	—	—	—	—	—	—	—	—	—	X	—	X	X	—	—	—	
Confirm HIV test results provided to participant	—	X	—	—	—	—	—	—	—	—	—	—	—	—	X	—	X	—	—	X	
Mucosal biopsy collection^g																					
Colorectal	—	X	—	—	—	—	—	—	—	—	—	—	—	X	X	X	X	—	—	—	
Cervical	—	X	—	—	—	—	—	—	—	—	—	—	—	X	X	X	X	—	—	—	
Vaginal	—	X	—	—	—	—	—	—	—	—	—	—	—	X	X	X	X	—	—	—	
Mucosal secretion collection^h																					
Semen	—	X	—	X	X	—	X	—	X	—	—	X	—	X	X	X	X	—	—	—	
Cervical secretions	—	X	—	X	X	—	X	—	X	—	—	X	—	X	X	X	X	—	—	—	
Rectal secretions	—	X	—	X	X	—	X	—	X	—	—	X	—	X	X	X	X	—	—	—	

Grayed out visits are not applicable to this group

^a Screening may occur over the course of several contacts/visits up to and including visit 02, prior to biopsy collections.

^b Includes transmission risk reduction counseling for HIV-infected participants.

^c Pregnancy prevention assessment is required only for participants who were born female and are capable of becoming pregnant.

^d Not applicable to HIV-infected participants.

^e Participants will be randomized prior to the first infusion, ideally within 4 days. See Section 6.2.

^f Includes pre-test counseling. A subsequent follow-up contact is conducted to provide post-test counseling and to report results to participant. If a participant has a confirmed diagnosis of HIV infection, do not perform HIV infection assessment.

^g Mucosal specimens will be collected once the participant has been found to have met mucosal specimen collection criteria specified in the SSP. Mucosal biopsy collections must be at least 28 days from the previous biopsy collection.

Procedures at HVTN CRS for Group 1 and Group 2 continued

Visit:	01	02	03	04	05	06	07	08	09	10	11	12	13	14	15	16	17	18	19	Post	
Day:		D-14	D0	D1-15	D29-43	D56	D57-71	D84	D85-99	D99-113	D112	D127-141	D168	D169-183	D197-211	D253-267	D351-365	D442-456	D526-540		
Week:		W-2	W0	W1-2	W5-6	W8	W9-10	W12	W13-14	W15-16	W16	W19-20	W24	W25-26	W29-30	W37-38	W51-52	W64-65	W76-77		
Month:			M0			M2		M3			M4		M6								
Procedure	Scr.		Infl			Inf2					Inf3		Inf4								
Local lab assessments^a																					
Screening HIV test	X	—	—	—	—	—	—	—	—	—	—	—	—	—	—	—	—	—	—	—	

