### **8.5. Analyses of mAb concentration and functional responses**

#### **8.5.1. General approach**

For the statistical analysis of lab endpoints, data from enrolled participants will be used according to the initial randomization assignment regardless of how many infusions they received. Additional analyses may be performed, limited to participants who received all scheduled infusions per protocol. Assay results that are unreliable, or from HIV-infected participants postinfection will be excluded. Since the exact date of HIV infection is unknown, any assay data from blood draws 4 weeks prior to an infected participant's last seronegative sample and thereafter may be excluded. If an HIV-infected participant does not have a seronegative sample postenrollment, then all data from that participant may be excluded from the analysis. Assay results that are from specimens collected outside of the visit window are generally also excluded unless otherwise noted in analyses (e.g., population pharmacokinetics analyses of concentrations over time) that account for the actual date of specimen collection.

For continuous assay data (eg, serum concentration of VRC01), graphical and tabular summaries of the distributions by treatment arm and timepoint will be made. Scatterplot matrix with correlation coefficient information between each pair of serum and mucosa drug levels at different timepoints will be provided. An appropriate data transformation (eg, log transformation) may be applied prior to testing to better satisfy analysis assumptions. Inference from these analyses would be limited by the small sample sizes of the groups.

For qualitative assay variables (eg, positive or negative), the analyses will be performed by tabulating the frequency of positive responses for each assay by group at each timepoint at which an assessment is performed. Crude response rates will be presented with their corresponding 95% confidence interval estimates calculated using the score test method [66].

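### In Groups 1-3 no HIV test is scheduled between screening and the visit after the last infusion, so scheduled testing cannot trigger the rule that stops infusions on HIV infection

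*Protocol*

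**What the plan says.** **Stopping rules.** Protocol Section 9.14: "If a participant becomes HIV-infected during the course of the study, no additional study product will be administered". Section 7.3.3 puts HIV infection on its list, introduced by "Specific events that will result in stopping a participant's infusion schedule include". Section 9.7 says the same of participants identified as infected after enrollment. Under Section 7.3.5 a participant's "biopsy collections will be permanently discontinued" for several reasons, of which HIV infection is one.

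**Infusions.** Groups 1 and 2 are infused "at Month 0, Month 2, Month 4, and Month 6" (Section 8.1), that is, at Visits 3, 6, 11 and 13 (days 0, 56, 112 and 168). Group 3 is infused at Visits 3, 8 and 13 (days 0, 84 and 168).

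**Testing.** The screening HIV test is at Visit 1. The row "HIV infection assessment" is marked at Visits 14, 16 and 17 in Appendix L (Groups 1-2) and at Visits 14, 16, 17 and 19 in Appendix M (Group 3). Groups 4 and 5 have it from Visit 9 (days 85-99) in Appendices N and O. Section 9.4 lists no HIV test at infusion visits, only a check that earlier results were given. Section 9.11 lets staff test at their discretion. Section 9.7.1 has staff advise participants to "confine their HIV testing while in the study to that provided through the CRS".

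**Analysis.** SAP 8.5.1, like Protocol 6.4.4.1: "If an HIV-infected participant does not have a seronegative sample postenrollment, then all data from that participant may be excluded".

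**The concern.** The groups with later infusions that a positive test could stop have no scheduled test while those infusions are being given. Groups 4-5, with no second infusion to stop, are tested mid-study. The untested interval in Groups 1-3 opens with the day -14 biopsies, and Protocol Section 4.8 says biopsy wounds may raise HIV risk, if exposed, until they heal. The advice to test only at the site makes an outside diagnosis less likely.

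Two things are at stake. A participant infected early could receive further antibody infusions with no scheduled opportunity to find out. In the analysis, a first positive at Visit 14 meets the condition for dropping all of that participant's assay data, including the primary drug-level data, even if the infection is recent.

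**Working it through.** **1. Where the tests are.** The rows in Appendices L and M have 20 columns (Visits 1-19 and Post). Counting along them gives Visits 14, 16, 17 and Visits 14, 16, 17, 19.

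**2. Check against blood volumes.** The HIV tube rows in Appendices H and I are hard to read, so I rebuilt each visit total from the other rows plus 10 mL per biopsy visit (footnote 16) and looked at what was left.

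- Appendix H, rows other than HIV: 5 + 5 + 5 + 30 + 30 + 42.5 + 5 + 561 + 153 + 50 = 886.5 mL. Stated visit totals exceed the rebuilt ones, beyond rounding, only at Visits 14 (90 against 79.5), 16 (90 against 79.5) and 17 (124 against 103.5). These are tubes of 10, 10 and 20 mL. Total 886.5 + 40 = 926.5 against 927 stated.
- Appendix I, same method: 5 + 5 + 5 + 25 + 25 + 59.5 + 5 + 552.5 + 153 + 70 = 905 mL. The excess is at Visits 14, 16, 17 and 19 (10, 10, 10 and 20 mL). Total 905 + 50 = 955 against 955 stated. The cell-storage row's total of 153 needs one more 34 mL entry than is legible; I placed it at Visit 14. This does not affect Visits 2-13.

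Neither appendix leaves room for an HIV tube at Visits 2-13.

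**3. Length of the gap.** Enrollment is day -14 and eligibility may be established up to 56 days earlier: -14 - 56 = day -70.

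- Shortest: 169 + 14 = 183 days.
- Longest: 183 + 70 = 253 days.

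**4. Infusions inside the gap.** Repeat infusions: 23 x 3 + 23 x 3 + 7 x 2 = 152, with Group 3 at the SAP's n = 7. With the protocol's approximate 6 it is 69 + 69 + 12 = 150. A scheduled post-enrollment test can stop none of them.

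**5. Biopsies.** In Groups 1-3, biopsies after Visit 2 resume at Visit 14. The Visit 14 biopsies share a visit with the first test. A positive at Visit 14 can stop those from Visit 15 on, and a positive at Visit 16 those from Visit 17 on.

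**6. The data rule.** It turns on a seronegative sample, not a scheduled test. Serum is stored at Visits 4, 5, 6, 7, 9, 11, 12 and 13 in Groups 1-2 and at Visits 4, 5, 8, 10 and 13 in Group 3. If stored Visit 13 serum (day 168) tested negative, the rule's 4-week margin would put only data from day 168 - 28 = 140 onward at risk, instead of everything. Neither document provides for such testing.

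**The case against.** **No contradiction.** A reader might infer that dosing an undiagnosed participant breaks the protocol's own rule. The documents do not support that. The rules can act only on an infection that has been found, as Section 9.7 makes explicit, and none promises a test before each infusion. Starting scheduled tests when biopsies resume is a coherent choice. Groups 4-5 are not held to a uniformly stricter standard: their Visit 4 and 5 biopsies precede any post-enrollment test.

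**Other safeguards exist.** A reader might also infer that any infected participant would finish the course undiagnosed. That is too strong. Volunteers must be assessed as low risk, and counseling is given at every attended visit. Behavioral risk is assessed at infusion Visits 11 and 13 (Groups 1-2) and 8 and 13 (Group 3). Chlamydia and gonorrhea are tested at Visit 9 or 10, abstinence is required after biopsies, and staff may test at any time. The testing algorithm cited in Section 9.7 is not in the documents; Section 14 describes it as for diagnosis, and visit timing is in the appendices.

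**Data loss is permitted, not certain.** The exclusion wording is permissive and stored samples exist.

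**A new tube has limits.** Appendices L and M let infusions proceed without results other than pregnancy tests, so a sample taken at an infusion visit need not affect that day's infusion. Diagnostic samples go to central laboratories. Group 3 enrollment was capped in November 2017 (SAP Section 6). Even a participant enrolled on 30 November would reach day 168 about 14 + 168 = 182 days later, around the end of May 2018, before Protocol Version 2.0 of 3 August 2018.

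All of this stands, and it limits the claim. It does not supply a scheduled trigger for the infusion stop.

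**Conclusion.** The point holds for scheduled testing and the infusion stop in Groups 1-3. For 183 to 253 days no scheduled test can activate that stop; it depends on discretionary testing, risk assessment or an outside diagnosis. The biopsy stop is only partly affected.

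The expected number of cases is small. The documents give no incidence. If one assumes 0.1% to 1% per year, 53 participants (23 + 23 + 7) and about 0.5 year, the expected number of infections is 53 x 0.5 x 0.001 = 0.03 to 53 x 0.5 x 0.01 = 0.27.

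One full exclusion in Group 1 or 2 would remove one of 10 men or 13 women in that arm. The 15% missing-data allowance in Protocol Section 6.1 (1.5 of 10; 1.95 of 13) would absorb a single loss if little else were missing. The case for change is therefore an inexpensive gain in participant safety and a clearer exclusion rule, not a threat to the trial's main results.

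**What to change.** 1. Reconcile Sections 7.3.3, 9.7 and 9.14 with the HIV-testing rows of Appendices H, I, L and M, so that at least one scheduled test, on an infusion-phase blood draw that already exists, can return a result before a later infusion. Which visits, and how results are handled before dosing, are for the sponsor to decide. The choice should allow for laboratory turnaround and for the appendix footnote on dosing without results. For Group 3 the change is probably only one of consistency.

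2. Add to Protocol 6.4.4.1 and SAP 8.5.1 wording such as: *Before assay data from an HIV-infected participant are excluded, stored post-enrollment samples will be tested to identify the last seronegative sample; results excluded under this rule will be reported by group.* The sponsor should confirm that stored serum or ACD plasma suits the diagnostic assay, since scheduled diagnostics use EDTA tubes. This part remains useful even if infusions are complete.

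**Cost.** One or two extra HIV assays and result-return contacts per participant in Groups 1-3, with no new visit. The highest 56-day blood total in Appendices H and I is 288 mL. Two more 10 mL tubes in that same window would make 308 mL, against the 500 mL limit in Section 10.2. Stored-sample testing is needed only if an infection occurs.
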